View: SF - Communication Plan for Research Team

Communication Plan for Research Team

1. * Describe the process that will be used to ensure that all persons at all involved sites assisting with the research are adequately informed about the protocol and their research related duties and functions:

VCU will be the only site for the study. All study personnel have completed CITI training. All study personnel will meet with the PI prior to the initiation of the study and every 6 months thereafter during study progress meetings. Additional training will be conducted as needed in response to any changes in the study protocol. Study personnel will be instructed to call and/or page the PI [name] directly with any adverse events or other problems with the study conduct.

IRB Panel Setup

1. * To which IRB is this study being submitted for review:

VCU IRB
 Western IRB
 NCI Central IRB
 Other IRB

2. If Other IRB, name the IRB that will review this research. If ORSP has not already agreed to rely on this IRB (via phone or email communication), you are strongly advised to contact [contact] before proceeding with this submission:

Review Setup

1. * Does this study involve greater than minimal risk:

Yes
 No

2. * Review Type Requested: (subject to IRB approval)

Full Board
 Expedited
 Exempt

3. * Has this protocol received a Massey protocol review:

Yes
 No

4. * Has this human subjects protocol (not the grant application) been reviewed by the funder:

Yes
 No

Research Description

1. * Describe the study hypothesis and/or research questions. Use lay language whenever possible.

Treatment with intravenous (IV) vitamin C in patients who are undergoing a non-invasive catheter ablation procedure to treat their atrial fibrillation (AF, a form of irregular heart beat) will be safe, well tolerated, and may lead to a reduced level of inflammation after the procedure.

2. * Describe the study's specific aims or goals. Use lay language whenever possible.

This will be a double-blinded, placebo-controlled pilot study to measure the effects of IV vitamin C in patients who are being scheduled for AF ablation (N=20). The primary endpoints will be evaluation of the safety of the IV vitamin C infusion and it's efficacy in reduction of inflammatory markers in the blood of patients undergoing AF ablation.

3. * Describe the study's background and significance, including citations, or upload a citation list in document upload. Use lay language whenever possible.

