Patients will be screened for eligibility, consented, and enrolled during their electrophysiology clinic appointment (standard of care) preceding their scheduled ablation. Based on prior experience with high dose IV ascorbic acid and the study focus on inflammatory effects, a limited list of exclusion criteria will include: diabetes mellitus with poor control or requiring insulin therapy (due to concerns that the infusions may interfere with glucometer readings), active renal calculus, active acute or chronic infection (including HIV and hepatitis C), active or recent (within 5 years) malignancy, autoimmune or auto-inflammatory disease, and recent or active use of immunosuppressive medications.

Upon admission for their ablation (standard of care), subjects will begin the first study infusion (sterile L-ascorbic acid diluted in 50mL of 5% dextrose in water or matched placebo of 50mL 5% dextrose in water). Once the subject has demonstrated no adverse effects of the first infusion, the AF ablation will proceed as scheduled. Patients will continue receiving infusions every six hours (+/- 3 hours) for a total of four infusions (research intervention). Of note, this 24 hours' worth of infusions was chosen as opposed to the 4 days' worth of infusions which was approved under the original IND (attached), since patients who are undergoing routine AF ablations rarely stay in the hospital longer than 24 hours. The shorter duration of infusions is still expected to test the theoretical benefit, while exposing the patients to even less risk of adverse reactions to the study agent than the 4 days' worth of infusions that are granted under the IND.

Prior to the first infusion, blood samples will be taken to measure plasma levels of ascorbic acid, biomarkers of inflammation (high-sensitivity C-reactive protein [hsCRP], interleukin-6 [IL-6]), and markers of blood vessel damage (von Willebrand Factor [vWF]), all part of the research intervention. A basic metabolic profile will be measured prior to the first infusion (standard of care), followed by measures of kidney function at 24 hours (+/- 12 hours) and at 30-day (+/- 14 days) follow up visit (research labs).

Patients will be monitored during their admission and during their follow up visit for any changes in blood pressure or heart rate, or any other reaction felt to be potentially related to the ablation procedure; monitoring for these elements in the history/physical

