2. * Explain how you will notify and obtain support from patient care providers in the units where the study will be conducted:

Patients will primarily be recruited during their visits with their electrophysiology specialists, who will be involved with their clinical care during the entirety of the study subjects' participation in the clinical trial. The study team will perform an in-service educational session for the staff in the clinical areas involved (clinic, electrophysiology suite, inpatient units) to include information about the study and the potential side effects of the vitamin C infusions. Given the prior interference noted with point of care blood glucose measurements, a blood glucose monitoring plan will be emphasized. As an extra precaution, the study exclusion criteria prohibits insulin-dependent or uncontrolled diabetic patients to minimize this risk overall.

ID: MS6_HM20006786

[View: SF - Study Funding](#)

Study Funding

1. * Have you applied for funding:

Yes
 No

2 If so, is this study already funded:

Yes
 No

ID: MS6_HM20006786

[View: SF - Funding Details](#)

Funding Details

1. * Select all funding sources for this study (pending or awarded):

Industry
 Direct Federal
 Non-Profit
 Indirect Federal
 State/Local Government
 Internal Grant
 Investigator/Departmental Funds
 None
 Other

2. Select all related proposals:

RAMS-SPOT ID# (FP/PT/PD#)
There are no items to display

Sponsor PI Title Status Start End

ID: MS6_HM20006786

[View: SF - Study Population](#)

Study Population

1. * Provide the total number of individuals at VCU, and at other sites under the VCU IRB, that:

1. May participate in any study interaction or intervention (including screening, consenting, and study activities)
AND/OR
2. You may obtain any data/specimens about (regardless of identifiability)

See the help text for additional guidance.

25

2. If this is a multi-Center Project, what is the total anticipated number of subjects across all sites:

N/A

3. * Provide justification for the sample size:

This is a pilot study, and it is difficult to estimate the needed sample size.
We believe that completing a 20-patient study will allow to measure effect size and either show a clear rise in ascorbic acid levels or allow for an accurate determination of the needed sample size.

4. * List the study inclusion criteria:

- 1) Age >= 21 years
- 2) Diagnosis of atrial fibrillation with plans for a catheter-based ablation procedure

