Disease-specific concerns related to the infusions include: interference with point of care glucometer readings (resulting in falsely high results), which is not seen in venous laboratory glucometer readings. In large doses of vitamin C, hyperoxaluria can be observed in 1-10% of patients, raising concerns primarily for patients with active renal calculus or those prone to recurrent renal calculi. Studies involving patients with advanced cancer have reported infrequent side effects consisting of nausea, vomiting, dizziness, and headache.

Other potential risks of participating in the research study include the mild risks of blood draws (bleeding, infection, damage to soft tissue). To minimize this, research-related blood draws will be taken from existing intravenous catheters placed for standard of care purposes (if applicable) or combined with clinically-indicated lab draws to avoid repeat phlebotomy.

2 * Describe how the risks / harms will be minimized:

Diabetics will be excluded if they are on insulin therapy and/or if they have uncontrolled diabetes, defined as a glycosylated hemoglobin of greater than or equal to 8%. While admitted periprocedurally, signs will be posted inside and outside of the patient rooms as a warning that point of care glucose readings should not be considered reliable within 36 hours of the infusion, in case this is ordered clinically. In-services will be given to the nursing staff in all involved clinical areas to educate them on the effect of high dose ascorbic acid infusions on point of care glucometers.

Patients with active renal calculus or those deemed prone to recurrent renal calculi will be excluded from the study.

Below is our protocol for addressing the blood glucose monitoring concerns:

Guidance for blood glucose monitoring in patients enrolled in investigational Vitamin C Studies under this IND:

Glucose levels in this study population are checked daily as standard of care, and point of care testing is not usually needed. However, all studies under this IND follow the glucose monitoring plan outlined below. If additional glucose draws are required for a participant in this study, all additional draws outside of standard of care will be billed to the study. Additional glucose draws, if needed, will be determined on an as needed basis by the clinical team.

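### The monitoring sentence ties other reactions to the ablation and leaves out the study infusion, and the remaining safety rules close the gap only in part

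*Protocol*

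**What the plan says.** Research Description, item 2 sets the aim: "The primary endpoints will be evaluation of the safety of the IV vitamin C infusion", together with the effect on inflammatory markers. Item 3 adds that patient symptoms will be followed as part of showing that the infusions are safe.

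Item 4 gives the procedure in one sentence with two parts. The part on vital signs applies to the admission and to the follow-up visit and names no cause. The part on everything else is limited by cause: "or any other reaction felt to be potentially related to the ablation procedure". The protocol describes these elements as belonging to the routine history and physical examination.

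The Risks section, item 1, names the infusion effects of interest. It lists "infrequent side effects consisting of nausea, vomiting, dizziness, and headache", reported in patients with advanced cancer, and states that "hyperoxaluria can be observed in 1-10% of patients" at large doses. Item 9 of the same section makes stopping depend on a participant having an effect known to be associated with the infusions.

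**The concern.** The primary safety question is about the infusion, but the sentence that tells the team which reactions to look for names only the ablation. It is the only procedural statement covering both the admission and the follow-up visit, so a reader following the protocol would apply an ablation test where an infusion test, or no causal test, belongs.

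Two things depend on complete capture: the comparison of infusion safety between arms, and the stopping criterion, which can act only on effects that someone has noted. In a blinded trial the clinician does not know who received vitamin C, so judging cause patient by patient is weak evidence. The comparison is sound only if events are recorded in the same way in both arms without first being sorted by presumed cause.

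**Working it through.** There is no power, alpha or event-rate figure to reproduce. The check is to set each safety provision against the question: would a mild infusion effect, such as one of the four named symptoms, be recorded?

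| Provision | Where | Looks at the infusion? | Limit |
|---|---|---|---|
| Monitoring sentence | Research Description, item 4 | Vital-sign changes: any cause. Other reactions: ablation only | Infusion not named |
| "Once the subject has demonstrated no adverse effects of the first infusion, the AF ablation will proceed as scheduled" | Research Description, item 4 | Yes | First of four infusions only |
| Kidney function at 24 hours and 30 days | Research Description, item 4 | Any cause | Laboratory value; does not record symptoms |
| Staff in-service | VCU Health System, item 2 | Yes | Informs staff; sets no recording rule |
| Daily check for adverse experiences | Risks, item 10 | Any cause | Runs from consent to study hour 24 |
| Adverse event form | Risks, item 10 | Any cause | Only what is both clinically important and unexpected |
| Reportable event, category 1 | Risks, item 10 | Any cause | Clinically important and unlike the expected course after ablation |
| Reportable event, category 2 | Risks, item 10 | Yes | Clinically important and thought to be linked to study drug or procedures |
| Reportable event, category 3 | Risks, item 10 | Yes | Serious, unexpected and related; to study hour 48 |
| Chart review for 12 months | Research Description, item 4 | Any cause | Only what routine care wrote down |
| Calls at 3 and 12 months | Research Description, item 4 | Any cause | Long after the infusions |

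**Timing of the any-cause check.** Four infusions six hours apart start nominally at 0, 6, 12 and 18 hours. The protocol allows +/- 3 hours but does not say whether that applies to each interval or to the nominal times. Taking study hour 0 as the start of the first infusion (an assumption):

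- Window on nominal times: latest fourth start = 18 + 3 = 21 hours, which leaves 24 - 21 = 3 hours of the daily check.
- Window on each interval: latest fourth start = 3 x (6 + 3) = 27 hours, which is 3 hours after the check has ended.

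So at the late edge of the window the last infusion gets at most 3 hours of any-cause observation, and possibly none. On the nominal schedule it gets 24 - 18 = 6 hours.

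**The 30-day visit.** With its +/- 14 days it falls between day 16 and day 44, after the daily check and the hour-48 window have both closed. Item 4 describes it as routine post-ablation follow-up plus safety laboratory tests and vitamin C levels. The only text saying which reactions to look for there is the ablation-framed sentence. Chart review would pick up a complaint the clinician documented, but nothing shown asks the clinician to document a mild one thought to be unrelated to the ablation.

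**A mild symptom traced through the rules.** If it is attributed to the infusion, it lies outside the monitoring sentence and reaches category 2 only if judged clinically important. If it is attributed to the ablation, it is within the monitoring sentence but can fail category 1 because it is expected after that procedure. Either way it can be seen and not recorded.

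**The case against.** The strongest reply is that the sentence describes routine clinical observation, while the adverse-event rules sit in the Risks section and do cover the study drug. Much of that stands, and it rules out three stronger readings that a reader might infer.

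- *Staff are not told to look for vitamin C effects.* Not supported. The in-service for clinic, electrophysiology suite and inpatient staff is "to include information about the study and the potential side effects of the vitamin C infusions".
- *Every reaction must pass an ablation test to be captured.* Not supported. Vital-sign changes carry no causal condition, the first infusion has its own check, the daily determination is any-cause, and the second reportable category names the study drug. The daily check and the phone calls are active contacts, so it would also be wrong to say that capture rests on volunteered complaints alone.
- *The quoted 1-10% measures the loss.* Not supported. With 20 patients and an assumed 1:1 allocation, 10 x 1% = 0.1 and 10 x 10% = 1 expected cases of hyperoxaluria. That is a laboratory finding, not a stone or a symptom. Neither the sentence as written nor a symptom question would detect it, so the figure says nothing about events missed through this wording.

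It is also fair to say that the data collection forms are not shown. They may already prompt for symptoms, so the lack of a checklist cannot be called an omission.

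What the reply does not remove is the mismatch itself, or the fact that the covering provisions end early or filter on importance, expectedness or attribution.

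**Conclusion.** The point holds as a misdirected sentence that the rest of the protocol only partly corrects. It should be fixed, but it does not show that infusion safety goes unmonitored. The exposure is confined to mild infusion effects that fall outside the first-infusion check and the any-cause daily check, chiefly those around or after the last infusion and those mentioned at the 30-day visit. Serious or clinically important events thought to be related to the study drug have a reporting route.

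No number of lost events can be given: the protocol describes the four symptoms only as infrequent and states no rate for stones. The conclusion assumes that the unseen data collection forms do not already override the sentence, and the timing figures assume that study hour 0 is the start of the first infusion.

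**What to change.** Reword the monitoring sentence in Research Description, item 4, so that during admission and at the follow-up visit any reaction is recorded whatever its suspected cause, in the same way in both arms. Record attribution to the infusion and attribution to the ablation as two separate items. Reconcile the sentence with items 2 and 3 of the same section, with the in-service text under VCU Health System, and with items 9 and 10 of the Risks section, so that what is observed, recorded and reported follows one rule.

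Optionally, unless the data collection forms already do this, add a short prompt list of the four symptoms named in Risks, item 1, asked identically in both arms at the infusions and at the 30-day visit.

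The core change is one sentence and two attribution fields at contacts already scheduled. The cost is more minor symptoms recorded in both arms. This concerns data capture only; it does not touch dosing, clinical management or the stopping criterion.

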We hypothesize that high dose intravenous ascorbic acid (Vitamin C) given around the time of AF ablation will be safe, well tolerated, efficacious in raising plasma ascorbate levels, and will blunt the amount of blood vessel damage, platelet activation, and overall acute inflammatory response, thus reducing the likelihood of early AF recurrence and post-ablation pain. We plan to evaluate high dose IV ascorbic acid in randomized, controlled, double-blinded safety and feasibility pilot study. Patients will be monitored before, during, and after their AF ablation, as well as in clinic follow up. Laboratory biomarkers, patient symptoms, and objective clinical endpoints will be tracked to determine the effects of the infusions to demonstrate their safety and efficacy in raising vitamin C levels. Based on the clear link between inflammation and AF (including recurrence after ablation), studies suggesting a link between vitamin C levels/supplementation and AF incidence, and extensive safety data in both cardiac stenting populations and severely ill septic/burn patients, we believe there is adequate background information to justify this pilot study in human subjects without conducting studies in animal models of AF ablation. We believe that this pilot study will provide an estimate of the potential effect of vitamin C infusions for the design of a future phase II study.

4. * Describe the proposed research using language understandable to those IRB committee members whose expertise is not scientific. The description must include:

- A statement explaining the study design
- A detailed description of all the procedures that will be followed to carry out the study, preferably in sequential order
- A description of all research measures/tests/interventions that will be used (if applicable)
- A detailed description or list of all secondary data elements and/or secondary specimens that will be obtained and how they will be used (if applicable)

See the help text for additional guidance.

We propose a single-center, double-blinded, randomized, controlled, safety and feasibility pilot study of high dose IV ascorbic acid (200mg/kg) over 24 hours, divided into four doses administered every six hours with a 30 minute IV infusion time per dose, compared to matched placebo infusion.

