exam are standard of care. A validated tool will be used to assess postprocedural pain on a 1-10 scale (research intervention; pain assessment tool attached). We hypothesize that vitamin C infusions will reduce inflammation, which will in turn reduce the amount of post-procedure pericarditis and thus the pain associated with the pericarditis. This is a small pilot study, and we recognize that it will not be powered for clinical outcomes or changes in "soft" endpoints such as subjective pain levels after the procedures. We focused the design of the study on "hard" endpoints such as inflammatory biomarkers, as we expect to be better powered to detect a difference with this. However, we still plan to obtain pain scores by the validated tool we uploaded, to demonstrate feasibility of this approach for future larger studies, and to gather hypothesis-generating data on any trends we may observe in pain reduction (again, to aid in the design of future studies).

Patients will have a 48 hour Holter monitor approximately 2 weeks after the procedure, to screen for recurrence of atrial arrhythmias (standard of care). They will return for a 30-day (+/- 14 days) follow up visit in the electrophysiology clinic for a standard post-ablation assessment (standard of care), as well as safety labs and repeat vitamin C levels (research labs). The medical charts will be monitored by the research team for the 12 months following the AF ablation, as the patients follow up with their (standard of care) visits. Any documented information on Adverse Events, AF recurrence or clinically significant postprocedural pain will be recorded. This will provide hypothesis-generating data and help design future larger scale Phase II studies. Subjects will be called on the phone to assess for Adverse Events, AF recurrence, or postprocedural pain at the 3 month and 12 month mark.

5. Upload any supporting tables or documents (e.g. protocol documents, figures/tables, data collection forms, study communications/reminders):

ID: MS6_HM20006786

View: SF - Study Activities

Study Activities

1. * Select which study type best describes the majority of the study. Your response will help determine which IRB panel should review this.

- Bio-Medical
- Qualitative - Social/Behavioral/Education (SBE)
- Quantitative - SBE
- Mixed Method - SBE
- Mixed Method - Biomedical

2. * This study will involve (check all that apply):

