 Facsimile Numbers
 E-mail Addresses
 Medical Record Numbers
 Device Identifiers
 Biometric Identifiers
 Web URLs
 IP Addresses
 Account Numbers
 Health Plan Numbers
 Full Face Photos or Comparable Images
 License/Certification Numbers
 Vehicle ID Numbers
 Other Unique Identifier
 No Identifiers
 Employee V#

3. If "Other Unique Identifier" was selected above, describe the identifiers:

4. * Will participants be able to withdraw their data (paper, electronic, or specimens) from the study if they no longer wish to participate:

Yes
 No

5. If yes above, describe how participants will be able to withdraw their data:

ID: MS6_HM20006786

[View: SF - Sample Collection](#)

Sample Collection

1. * Select all of the types of samples that will be collected as part of this study:

- Amniotic Fluid
- Blood
- Buccal Smears
- Saliva
- Tissue
- Urine
- Other
- None of the Above

2. If Other, please describe the type of sample being collected:

3. * Describe how the samples will be collected and the collection schedule. For each type of sample, include information about

- The procedures that will be followed to collect the sample
- The role(s) of the individuals who will collect the sample
- The volume/size range of the sample
- The timing and frequency of sample collection

All blood samples will be collected by trained personnel (e.g. physicians, nurses, phlebotomists). Whenever possible, blood will be obtained at the same time as other clinically indicated blood draws—or through indwelling catheters—to minimize the need for additional venipuncture. Labs for the study will be drawn at baseline (before the ablation procedure and before any IV vitamin C has been administered), 24 hours (+/- 12 hours) after the start of the first vitamin C infusion, and at the 30-day (+/- 14 days) follow up clinic visit. At each study visit, 2-3 tablespoons will be drawn.

4. * Will Genetic Testing be conducted on any of the samples:

- Yes
- No

5. * Will any of the samples be used for a pregnancy test:

- Yes
- No

6. If yes, describe how positive pregnancy results will be communicated to the participant, particularly if minors are involved:

Women of childbearing potential will be informed (in person) of positive pregnancy tests. No minors will be allowed to participate in the study.

7. * Will any of the samples be used to screen or document alcohol or illicit drug use:

- Yes
- No

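### The only early post-treatment blood draw, allowed 12 to 36 h after the first infusion starts, can precede the end of the fourth infusion, nominally at 18.5 h

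*Protocol*

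**What the plan says.** **Draw.** Protocol, Sample Collection, item 3, schedules study labs at baseline, at "24 hours (+/- 12 hours) after the start of the first vitamin C infusion", and at the 30-day (+/- 14 days) visit. No other post-treatment research draw is described. The same item adds: "Whenever possible, blood will be obtained at the same time as other clinically indicated blood draws". It does not say when those clinical draws fall.

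**Infusions.** Under Research Description, item 4, the total dose is "divided into four doses administered every six hours with a 30 minute IV infusion time per dose". Later in that item: "Patients will continue receiving infusions every six hours (+/- 3 hours) for a total of four infusions". It does not say whether the tolerance applies to each nominal time or to each interval.

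**What is measured when.** Research Description, item 4, names hsCRP, IL-6 and vWF only before the first infusion. A basic metabolic profile is also taken then, "followed by measures of kidney function at 24 hours (+/- 12 hours") and at the 30-day visit.

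**Length of stay.** The same item says that "patients who are undergoing routine AF ablations rarely stay in the hospital longer than 24 hours".

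**Use of the data.** Research Description, item 2, makes reduction of inflammatory markers a primary endpoint alongside safety. Item 4 justifies the focus on biomarkers "as we expect to be better powered to detect a difference with this", and item 3 expects that "this pilot study will provide an estimate of the potential effect of vitamin C infusions for the design of a future phase II study". Study Population, item 3, looks to a 20-patient study to measure effect size.

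**The concern.** The intervention under test is the four-infusion course. The draw is timed from the start of the first infusion, with a tolerance wide enough to reach back before the last one. Two active-arm patients can both be on protocol, one sampled after three infusions and the other after four. The estimated contrast then mixes partial and full exposure, and no analysis can supply the full-course value that was never sampled. The next scheduled draw is day 16 at the earliest (30 - 14), so it cannot stand in for the acute measurement.

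At stake is the number that the pilot exists to produce: an early biomarker effect on which to plan phase II. The 24 h kidney-function lab carries the same window, so that safety measurement can also precede full exposure.

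**Working it through.** The protocol gives no figure for this overlap, so there is none to reproduce. The check is a timeline.

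**Inputs.** Draw at 24 +/- 12 h from the start of infusion 1 (Sample Collection, item 3). Four infusions of 0.5 h at 6 h intervals, with +/- 3 h (Research Description, item 4).

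**Draw window.** 24 - 12 = 12 h to 24 + 12 = 36 h, so 24 h wide.

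**Nominal schedule.** Starts at 0, 6, 12, 18 h; ends at 0.5, 6.5, 12.5, 18.5 h. Completed infusions: two at 12 h, three at 18 h, four at 24 h.

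**Share of the window before infusion 4 ends** = max(0, end of infusion 4 - 12) / 24.

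| Reading of the +/- 3 h | End of infusion 4 | Share of window before it | Target minus end (24 h - end) |
|---|---|---|---|
| Nominal, no deviation | 18.5 h | 6.5/24 = 27% | +5.5 h |
| Each nominal time, early | 15.5 h | 3.5/24 = 15% | +8.5 h |
| Each nominal time, late | 21.5 h | 9.5/24 = 40% | +2.5 h |
| Each interval, all 3 h | 3 x 3 + 0.5 = 9.5 h | 0% | +14.5 h |
| Each interval, all 9 h | 3 x 9 + 0.5 = 27.5 h | 15.5/24 = 65% | -3.5 h |

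A draw at exactly 24 h misses the end of infusion 4 only if total delay over the three intervals exceeds 24 - 18.5 = 5.5 h. That is possible only on the per-interval reading.

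**Infusion 3.** Only (12.5 - 12)/24 = 2% of the window precedes its nominal end, so sampling after only two infusions is an edge case.

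**A 24 h stay** (assumed to run from the first infusion). The in-hospital part of the window is 12-24 h, and 6.5 of those 12 h (54%) precede the nominal end of infusion 4.

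**Effect on the contrast.** If a fraction f of active patients is sampled early, and the contrast at that point is a fraction r of the full-course value, the expected estimate is [1 - f(1 - r)] times the full-course contrast. The documents give neither f nor r. The following illustration rests wholly on assumptions: effect proportional to infusions completed, and draws spread evenly.

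- Over 12-36 h: (0.5 x 2/4 + 6 x 3/4 + 17.5 x 1)/24 = 22.25/24 = 0.93.
- Over 12-24 h: (0.5 x 2/4 + 6 x 3/4 + 5.5 x 1)/12 = 10.25/12 = 0.85.
- If draws cluster at 24 h on the nominal schedule, or if the markers do not respond to the last infusion by the time of the draw, the factor is 1.

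These figures show how the mechanism works. They do not estimate its size in this trial.

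**The case against.** - **The markers are not named at 24 h.** True. Their measurement at this draw is inferred from the general reference to study labs in Sample Collection, item 3, and from the primary endpoint. The inference is reasonable, because a reduction needs a post-treatment value and this is the only early draw described. Forms or tables uploaded with the application might carry a tighter instruction, but the protocol text does not.
- **The target is 24 h, and staff will aim for it.** This stands as far as it goes: on the nominal schedule a 24 h draw follows all four infusions by 5.5 h. A reader might infer that 27% of patients will be sampled early. The documents do not support that, because they give no distribution of draw times. What stands is that early draws are compliant and that the text steers timing towards clinical draws.
- **A window anchored to the first infusion treats everyone alike.** This is a real merit. A rule that kept a different window for patients whose infusions stop early would make draw timing depend on an event after randomisation. The fix has to avoid that.
- **Drawing after infusion 4 does not fix the time since infusion 4.** Correct. Time since the last infusion will still vary, and no marker kinetics are given from which to set a minimum gap. The change ensures only that patients who complete the course are sampled after all of it.
- **In 20 patients, lost samples could cost more than the overlap.** This cannot be excluded, which is why the fix keeps out-of-window samples.

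**Conclusion.** The point holds as a weakness in a stated sampling window. A fully compliant early draw can precede completion of the course: 27% of the window nominally, 15-40% or 0-65% depending on how the +/- 3 h tolerance is read. It rests on the inference that the inflammatory markers are measured at this draw.

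The consequence is possible attenuation of the estimated full-course contrast, plus added variability in the active arm. The documents give no dose-response, marker kinetics or expected draw times, so its size cannot be derived from them. A reader might go further and infer a bias between arms or an invalid study. Neither follows: the same window applies to both arms under randomisation and blinding, so timing favours neither arm, and the 24 h target itself is sound on the nominal schedule.

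Severity is minor to moderate. It is worth changing because the correction is cheap beforehand and the missing values cannot be recovered afterwards.

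**What to change.** In Sample Collection, item 3, keep the 24 h target and the 36 h upper limit, but move the lower limit so that the early draw follows completion of the fourth infusion. Mirror this for the 24 h kidney-function lab in Research Description, item 4. Name the inflammatory markers explicitly at this draw if that is the intention.

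For patients whose infusions stop early but who remain in the study (Risks, Discomforts, Potential Harms and Benefits, item 2), use the same clock window: not before the scheduled end of the fourth infusion, nominally 18.5 h, and up to 36 h. Timing then does not depend on whether treatment was stopped. A sample outside the window is still taken and kept, with its actual time recorded.

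The window is never empty: 36 - 18.5 = 17.5 h nominally, 36 - 21.5 = 14.5 h if the fourth infusion is 3 h late, and 36 - 27.5 = 8.5 h if delays accumulate fully.

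**Cost.** One sentence in each of two places, and no extra visit for patients who complete the course, since they are present for the fourth infusion. For a 24 h stay the slot before discharge is at most about 24 - 18.5 = 5.5 h, and 2.5 h if that infusion is 3 h late. A few samples may fall out of window or need a separate draw.

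No change to the infusion schedule is proposed. The sponsor should reconcile the +/- 3 h tolerance with the 24-hour dosing period in the same item, since on the per-interval reading the fourth infusion can end at 27.5 h.
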